Recommended Dose Modifications any time during a cycle of therapy

Investigations (Hepatic^{})**

Bilirubin: total bilirubin without ALT/AST increase above baseline value (confirmed 48-72hr later)^c

Grade 1 (> ULN – 1.5 x ULN)	Maintain dose level of LGX818 and MEK162 (and LEE011 in patients treated in triple-combination arm) with LFTs monitored bi-weekly.
Grade 2 (> 1.5 – 3.0 x ULN)	Interrupt dosing of LGX818 and MEK162 (and LEE011 in patients treated in triple-combination arm) until resolved to Grade ≤ 1, then: - If resolved in ≤ 21 days, then maintain dose level of LGX818 and MEK162 (and LEE011 in patients treated in triple-combination arm) - If resolved in > 21 days, then ↓ 1 dose level* of LGX818 and MEK162 (and LEE011 in patients treated in triple-combination arm) - If not resolved within 28 days, or if toxicity recurs, discontinue patient from all study drug treatment. Repeat liver enzyme and bilirubin tests twice weekly for 2 weeks after dose resumption.
Grade 3 (> 3.0 x ULN)	Interrupt dosing of LGX818 and MEK162 (and LEE011 in patients treated in triple-combination arm) until resolved to Grade ≤ 1, then ↓ 1 dose level - Repeat liver enzyme and bilirubin tests twice weekly for 2 weeks after dose resumption - If not resolved within 28 days, or if toxicity recurs, discontinue patient from all study drug treatment.
Grade 4 (> 10.0 x ULN)	Discontinue patient from study treatment.

Note: If Grade 3 or 4 hyperbilirubinemia is due to the indirect (non-conjugated) component only, and hemolysis as the etiology has been ruled out as per institutional guidelines (e.g., review of peripheral blood smear and haptoglobin determination), then ↓ 1 dose level* and continue treatment at the discretion of the investigator.

AST or ALT without bilirubin elevation > 2 ULN (confirmed 48-72hr later)^c

Grade 1	Maintain dose level of LGX818 and MEK162 (and LEE011 in patients treated in triple-combination arm) and monitor LFTs biweekly.
---------	--

Recommended Dose Modifications for (dual) LGX818 and MEK162 or (triple) LGX818 and MEK162 and LEE011 combination study treatment

Worst Toxicity CTCAE v4.03 Grade (unless otherwise specified)^a

Recommended Dose Modifications any time during a cycle of therapy

AST or ALT without bilirubin elevation > 2 ULN (confirmed 48-72hr later)^c (continued)

Grade 2

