Interrupt dosing of LGX818 and MEK162 (and LEE011 in patients treated in triple-combination arm) until resolved to Grade ≤ 1 (or Grade ≤ 2 in case of liver metastasis), then:
 - If resolved in ≤ 21 days, maintain dose level of LGX818 and MEK162 (and LEE011 for triple-combination arm).
 - If resolved in > 21 days, then ↓ 1 dose level* of LGX818 and MEK162 (and LEE011 for triple-combination arm).
 - If not resolved within 28 days, discontinue patient from all study drug treatment.
Repeat liver enzyme and bilirubin tests twice weekly for 2 weeks after dose resumption.

Grade 3 (> 3.0 x ULN)

Omit dose of LGX818 and MEK162 (and LEE011 in patients treated in triple-combination arm) until resolved to ≤ baseline grade, then ↓ 1 dose level of dose level of LGX818 and MEK162 (and LEE011 in patients treated in triple-combination arm). If not recovered to ≤ baseline grade within 28 days, discontinue patient from all study drug treatment.
Repeat liver enzyme and bilirubin tests twice weekly for 2 weeks after dose resumption. If toxicity recurs, discontinue patient from all study drug treatment.

Grade 4 (> 10.0 x ULN)

Discontinue patient from study drug treatment.

AST or ALT and Bilirubin^d

For patients with normal ALT and AST and total bilirubin at baseline: AST or ALT > 3.0 x ULN combined with total bilirubin > 2 x ULN without evidence of cholestasis^e

Discontinue patient from study drug treatment.

For patients with elevated AST or ALT or total bilirubin at baseline: baseline: (AST or ALT > 2 x baseline AND > 3.0 x ULN) OR (AST or ALT 8.0 x ULN) — whichever is lower — combined with (total bilirubin > 2 x baseline AND > 2.0 x ULN)

Discontinue patient from study drug treatment.

Recommended Dose Modifications for (dual) LGX818 and MEK162 or (triple) LGX818 and MEK162 and LEE011 combination study treatment

Worst Toxicity CTCAE v4.03 Grade (unless otherwise specified)^a

Recommended Dose Modifications any time during a cycle of therapy

Investigations (Metabolic)

Asymptomatic amylase and/or lipase elevation

Grade 1 (> ULN – 1.5 x ULN)	Maintain dose level of LGX818 and MEK162 (and LEE011 in patients treated in triple-combination arm) and initiate appropriate medical therapy and monitoring.

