^d All patients with ALT or AST >5.0x ULN and total bilirubin > 1.5x ULN in the absence of cholestasis must immediately be withdrawn from study treatment and every attempt should be made to carry out the **liver event follow-up assessments** as described below in [Section 6.3.3](#).
If combined elevations of AST or ALT and total bilirubin do not meet the defined thresholds, please follow the instructions for isolated elevation of total bilirubin and isolated elevation of AST/ALT, and take a conservative action based on the degree of the elevations (e.g. discontinue treatment at the situation when omit dose is needed for one parameter and discontinue treatment is required for another parameter). After all elevations resolve to the defined thresholds that allow treatment re-initiation, re-start the treatment either at the same dose or at one dose lower if meeting a criterion for dose reduction

^e “Cholestasis” defined as: ALP elevation (>2.0 x ULN and R value (ALT/ALP in x ULN) ,2.0) in patients without bone metastasis, or elevation of ALP liver function in patients with bone metastasis.

^f All values refer to the average of triplicate measurements.

^g Ophthalmic monitoring mandated for retinal event, posterior uveitis, RVO: further evaluation with specialized retinal imaging (e.g. ocular coherence tomography, angiography).

^h Except: 1) lymphopenia unless clinically significant, 2) occurrence of KA and/or cutaneous SCC, 3) alkaline phosphatase, 4) AEs not considered clinically significant like alopecia study drug-related fever, electrolyte abnormalities (including K, NA, Cl, HCO₃, Mg, Ca, PO₄).

* ↓ 1 dose level refers to: next lower previously tested dose level of LGX818 and LEE011 and the next lower dose level of MEK162 (please see [Table 6-1](#) and [Table 6-2](#)).

Recommended Dose Modifications for (dual) LGX818 and MEK162 or (triple) LGX818 and MEK162 and LEE011 combination study treatment

**Worst Toxicity CTCAE v4.03 Grade
(unless otherwise specified)^a**

Recommended Dose Modifications any time during a cycle of therapy

** Confounding factors and/or alternative causes for increased transaminases should be excluded before dose interruption/reduction. They include but are not limited to: concomitant medications, herbal preparations or dietary supplements, infection, hepato-biliary disorder or obstruction, new or progressive liver metastasis, and alcohol intake.

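### A Table 6-4 footnote puts an open-ended search for other causes ahead of the dose hold, delaying it for confirmed isolated AST/ALT rises of Grade 2 (no liver metastasis) or Grade 3

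*Protocol*

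**What the plan says.** The hepatic heading of Table 6-4 (Protocol, Section 6.3.2) carries a double-asterisk footnote: "Confounding factors and/or alternative causes for increased transaminases should be excluded before dose interruption/reduction". Its examples run from co-medication and herbal products to liver metastasis and alcohol. The list is stated to be non-exhaustive, and there is no deadline and no limit by grade.

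The rows it qualifies are these.

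- The isolated transaminase block is headed "AST or ALT without bilirubin elevation > 2 ULN (confirmed 48-72hr later", so a repeat test is already built in.
- Grade 1: keep the doses "and monitor LFTs biweekly".
- The Grade 2 row reads: "Interrupt dosing of LGX818 and MEK162 (and LEE011 in patients treated in triple-combination arm) until resolved to Grade ≤ 1 (or Grade ≤ 2". The second, looser threshold is for patients who have liver metastasis.
- The Grade 3 row reads: "Omit dose of LGX818 and MEK162 (and LEE011 in patients treated in triple-combination arm) until resolved to". The stated target is the patient's baseline grade or lower, after which the dose goes down by one level.
- Both the Grade 2 and Grade 3 rows add: "Repeat liver enzyme and bilirubin tests twice weekly for 2 weeks after dose resumption".
- Grade 4: discontinue.
- Combined block, normal baseline: "AST or ALT > 3.0 x ULN combined with total bilirubin > 2 x ULN without evidence of cholestasis" means discontinuation. A second row covers patients with raised baseline values.

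Footnote d covers combined rises short of those criteria: "If combined elevations of AST or ALT and total bilirubin do not meet the defined thresholds, please follow the instructions for isolated elevation". It names both the bilirubin and the AST/ALT instructions and asks for the conservative choice. It also orders immediate withdrawal when ALT or AST exceeds 5 x ULN with bilirubin above 1.5 x ULN and no cholestasis.

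**The concern.** Looking for another cause before lowering a dose for good is sensible. Requiring it before a temporary hold reverses the safe order. The trigger for the hold becomes completed exclusion rather than the confirmed rise, and an open list with no deadline has no defined point of completion. A site that follows the footnote keeps all study drugs going in the meantime.

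The timing matters. Appendix 8 says that in most cases of drug-induced liver injury the transaminases rise days to weeks before bilirubin does. A confirmed isolated rise above 3 x ULN is therefore one half of the combined criterion that requires discontinuation, seen at the stage when a hold could still help.

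The risk is not limited to one drug. Section 1.2.2.2.1 reports a suspected case of fatal acute liver failure with MEK162 at 60 mg BID, a dose above the 45 mg BID in the declared dual-combination RP2Ds (Section 6.2.2). Section 1.2.3.1.2 names hepatic toxicity as a major potential toxicity of LEE011.

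**Working it through.** The protocol states no figure to reproduce. The check sets the passages side by side.

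**Rows reached.** The hepatic block has 4 bilirubin rows (Grades 1 to 4), 4 isolated AST/ALT rows (Grades 1 to 4) and 2 combined rows: 4 + 4 + 2 = 10. The footnote concerns raised transaminases, and the actions it conditions are interruption and reduction.

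- AST/ALT Grade 1 keeps the dose, so there is nothing to delay.
- AST/ALT Grade 2 calls for interruption: delayed. With liver metastasis, however, the resumption threshold is Grade 2 itself. Such a patient already meets it, with or without the footnote.
- AST/ALT Grade 3 calls for omission and then reduction: delayed.
- AST/ALT Grade 4 and both combined rows call for discontinuation, which the footnote does not mention.
- The bilirubin rows respond to bilirubin, which the footnote does not mention.

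Result: 2 of 10 rows, the Grade 2 row only for patients without liver metastasis.

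**Combined rises below the discontinuation criteria.** Footnote d applies both isolated sets of instructions. Bilirubin above 1.5 x ULN (Grade 2) calls for interruption in its own right, and the transaminase footnote does not hold that up. Bilirubin at or below 1.5 x ULN (Grade 1 or normal) keeps the dose, so any hold must come from the AST/ALT row, where the footnote applies. The delay therefore reaches combined rises only at or below 1.5 x ULN.

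**How the protocol orders the same steps elsewhere.**

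- QTcF Grades 2 and 3 (Table 6-4): dosing is interrupted and the cause-finding steps, including a review of co-medication, are done together.
- Amylase/lipase Grade 3 (Table 6-4): dosing is interrupted, with imaging due within 1 week of first occurrence.
- Section 6.3.3 (LEE011 patients, recommended only): much of the same work-up is follow-up of a rise that requires interruption, not a condition for interrupting.

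**Backstops.** The DLT rule (Table 6-3, Section 6.3.1) calls for interruption when AST/ALT stays at Grade 3 for more than 7 days. It covers Cycle 1 only and does not reach isolated Grade 2. Under Section 6.2.5 it also requires the event to be judged unrelated to disease, other illness and co-medication. The Grade 4 and combined-elevation rules act at a later stage of injury. None of these closes the gap.

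**The case against.** The strongest reply is that nothing forces a site to wait. The footnote uses advisory language, Section 6.3.1 says the dose may be adjusted, and Table 6-4 gives recommended modifications. Section 12.1 expects immediate action where a patient's safety needs it. Several listed causes, such as co-medication, herbal products and alcohol, can be checked by history during the 48-72 hour confirmation. Needless holds also have a price, since more than 21 days off drug generally ends treatment. All of this stands and limits the weight of the point. It does not make the written order right: a site that complies delays the hold.

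Three stronger readings are tempting, and the documents do not support them.

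- A reader might infer that footnote d brings every sub-threshold combined rise under the delay. It does not, because the bilirubin rows apply as well and the conservative choice is directed.
- A reader might infer that a patient kept on drug falls back to the recommended 4-weekly chemistry of Table 7-2. That overlooks several provisions. The block requires a repeat at 48-72 hours, and Appendix 8 asks for more frequent monitoring above 3 x ULN. Table 7-2 lists minimum procedures, and Appendix 7 obliges the investigator to do supplemental tests as medically indicated. The trigger in Section 6.3.3 can also be read as the grade of the rise rather than the act of stopping.
- A reader might infer a number of extra dosing days. The protocol gives no work-up duration from which to derive one.

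**Conclusion.** The point holds within these limits. As written, the footnote delays the hold for a confirmed isolated AST/ALT rise of Grade 2 without liver metastasis or of Grade 3, and for combined rises only with bilirubin at or below 1.5 x ULN. Its size is 2 of 10 hepatic rows, one in part. No monitoring ratio, count of dosing days or count of harmed patients is claimed.

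The rule applied to the 10 patients on treatment at Amendment 10 (5 dual, 5 triple). They are the patients it governs, not patients known to have such a rise. Enrolment is closed (Appendix 10), so the number is not growing.

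The conclusion assumes that a site follows the footnote literally, and that its reference to raised transaminases leaves the bilirubin rows outside it. The change should be made because it favours patient safety at little cost, but the advisory wording and the small number remaining keep it from being critical.

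**What to change.** Reword the footnote by amendment to: *Interrupt dosing as specified for the grade once the rise is confirmed, and evaluate confounding factors and alternative causes in parallel. Study drugs are resumed only when the recovery threshold in the row is met; if an alternative cause is established, the dose reduction may be omitted in discussion with the Sponsor. This does not change the Grade 4 row, the combined-elevation rows or the withdrawal rule in footnote d.*

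The recovery threshold must stay in the text. If finding another cause were enough to restart, full dosing could resume with AST/ALT still at Grade 3, which the present rows do not allow.

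The cost is one footnote and no new cause evaluation, since the footnote already asks for it. An earlier hold brings forward the weekly follow-up that Section 6.2.6 attaches to interruption. Some holds will prove unnecessary, and a few may run towards the existing limits. At Grade 2, recovery after more than 21 days means a dose reduction. At Grade 2 or 3, no recovery within 28 days means discontinuation. Under Section 6.3.2, an interruption beyond 21 days generally ends treatment unless there is objective clinical benefit. Allowing the reduction to be omitted when another cause is established softens part of this.

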6.3.3 Additional follow-up for hepatic toxicities in patients receiving LEE011

Hepatic toxicity monitoring includes the following LFTs: albumin, ALT, AST, total bilirubin (fractionated if total bilirubin > 2 x ULN), alkaline phosphatase (fractionated if alkaline phosphatase is grade 2 or higher) and GGT. For patients with Gilbert Syndrome: total and direct bilirubin must be monitored, intensified monitoring applies to changes in direct bilirubin only.

Close observation is recommended in case of AST, ALT, and/or bilirubin increase requiring dose interruption, which involves:

- Repeating liver enzyme and serum bilirubin tests **two or three times weekly**. Frequency of re-testing can decrease to once a week or less if abnormalities stabilize or return to normal values.
- Obtaining a more detailed history of current symptoms.
- Obtaining a more detailed history of prior and/or concurrent diseases, including history of any pre-existing liver conditions or risk factors.
- Obtaining a history of concomitant drug use (including non-prescription medications, herbal and dietary supplements), alcohol use, recreational drug use, and special diets.
- Ruling out acute viral hepatitis types A, B, C, D, and E; hepatotropic virus infections (CMV, EBV or HSV); autoimmune or alcoholic hepatitis; NASH; hypoxic/ischemic hepatopathy; and biliary tract disease.
- Obtaining a history of exposure to environmental chemical agents.
- Obtaining additional tests to evaluate liver function, as appropriate (e.g., INR, direct bilirubin).
- Considering gastroenterology or hepatology consultations.
- Assessing cardiovascular dysfunction or impaired liver oxygenation, including hypotension or right heart failure as possible etiologies for liver dysfunction.
- Considering a liver biopsy, as clinically indicated to assess pathological change and degree of potential liver injury.

6.4 Concomitant medications

6.4.1 Permitted concomitant therapy

The patient must be told to notify the investigational site about any new medications he/she takes after the start of the study drug combination. All medications (other than study drugs) and significant non-drug therapies (including herbal medicines, physical therapy and blood transfusions) administered during the study must be listed on the Concomitant medications/Significant non-drug therapies eCRF.

Patients taking concomitant medication chronically should be maintained on the same dose and dose schedule throughout the study period, as medically feasible. The days of full PK blood sampling should be representative of the other study days with regard to the use of the chronically administered concomitant medications. However, if a concomitant medication is used intermittently during the study, this medication should be avoided on the days of full PK sampling, if medically feasible.

The use of bisphosphonates regardless of indication is allowed for the LGX818 and MEK162 dual combination (prophylactic treatment is not allowed for bisphosphonates with LEE011) provided patients have been on stable doses for at least 2 weeks prior to study entry. Stable doses should be maintained during the treatment period. Patients requiring initiation of bisphosphonates during the course of the study should be discontinued due to progressive disease unless disease progression can be completely ruled out and this is clearly documented in the patients' source documentation.

Chronic dosing of corticosteroids such as dexamethasone and prednisone is known to lead to induction of CYP3A enzymes, thereby potentially increasing the risk of reducing drug exposure for CYP3A substrates to subtherapeutic levels. The following forms of corticosteroid treatment are permitted:

- Topical applications (e.g. rash), inhaled sprays (e.g. obstructive airway diseases), eye drops, or local injections (e.g., intra-articular);
- A short duration (< 5 days) of systemic corticosteroids \leq to the anti-inflammatory potency of 4 mg dexamethasone (e.g., for chronic obstructive pulmonary disease, or as an antiemetic).

Refer to the LGX818 Investigator's Brochure, MEK162 Investigator's Brochure and LEE011 Investigator's Brochure as applicable for information on possible interactions with other drugs.

Approved Covid-19 vaccines are permitted, including those under an EUA. The timing of COVID-19 vaccine administration is at the investigator's discretion. The administration of a COVID-19 vaccine would be recorded as a concomitant medication and standard AE collection and reporting processes would be followed.

